### 18.5.2. Trial Definitions

The trial definitions in this section should be used when recording data from procedure through study exit.

#### 18.5.2.1. NYHA Functional Classification

The New York Heart Association (NYHA) Functional Classification is a system for defining cardiac disease and related functional limitations into four broad categorizations as defined in the table below.

Classification	Description
Class I	Patients with cardiac disease, but without resulting limitations of physical activity. Ordinary physical activity does not cause undue fatigue, palpitation, dyspnea, or anginal pain.
Class II	Patients with cardiac disease resulting in slight limitation of physical activity. Patients are comfortable at rest. Ordinary physical activity results in fatigue, palpitation, dyspnea, or anginal pain.
Class III	Patients with cardiac disease resulting in marked limitation of physical activity. Patients are comfortable at rest. Less than ordinary physical activity causes fatigue, palpitation, dyspnea, or anginal pain.
Class IV	Patients with cardiac disease resulting in inability to perform any physical activity without discomfort. Symptoms of cardiac insufficiency or of the anginal syndrome may be present even at rest. If any physical activity is undertaken, discomfort is increased.

### 18.5.2.2. Endpoint Related Events

Death	
All-Cause Mortality All deaths from any cause after a valve intervention.

	
Cardiac Death All deaths resulting from cardiac causes. This category includes valve-related mortality, sudden unexplained deaths, and deaths from non-valve-related cardiac causes (e.g., heart failure, acute myocardial infarction, or documented arrhythmias).

	
Valve-related mortality Any death caused by structural valve deterioration, nonstructural dysfunction, valve thrombosis, embolism, bleeding event, or operated valve endocarditis; death related to reintervention on the study valve; or sudden, unexplained death. Deaths caused by heart failure in patients with advanced myocardial disease and satisfactorily functioning cardiac valves are not counted. Specific causes of valve-related deaths should be reported.

	
Sudden, unexplained death Death in which the cause has not been determined by clinical investigation or autopsy findings and the relationship to the study valve is undefined.

	
Non-Cardiac Death All deaths due to any cause, excluding cardiac death, sudden, unexplained death, or study valve-related mortality.

Explant	
Reintervention to remove of the study valve for any reason. Does not include peri-procedural removal during the index procedure.

Reintervention viii	
Following the completion of the index procedure, defined as the subject leaving the operating theater with an implanted Mosaic or Hancock II valve; Any surgical or percutaneous interventional catheter procedure that repairs, otherwise alters or adjusts, or replaces a previously implanted Mosaic or Hancock II valve bioprosthesis. In addition to surgical reoperations, balloon dilatation, interventional manipulation, repositioning, or retrieval, and other catheter-based interventions for valve –related complications are also considered reinterventions. Report indications for reintervention; surgical and percutaneous catheter reinterventions should be listed separately.

### 18.5.2.3. Valve-Related Adverse Events

Term	Valve-Related Adverse Event Definition
Prosthetic Valve Endocarditis viii	
Infection involving a heart valve substitute.
 
Diagnosis is based on customary clinical criteria, including an appropriate combination of positive blood cultures, clinical signs (fever, new or altered cardiac murmurs, splenomegaly, systemic embolus, or immunopathologic lesions), and/or histologic confirmation of endocarditis at reoperation or autopsy. Morbidity associated with active infection such as valve thrombosis, embolus, or paravalvular leak is included under this category and is not included in other categories of morbidity.
 
 
The Modified Duke Criteria for Endocarditis ixmay be used to diagnose endocarditis events for the HAMMOCK PAS study, in the absence of reoperation or autopsy. These criteria are provided for reference in Section 18.5.3 of this appendix.
 

Hemolysis	
Hemolysis is defined as laboratory evidence of red blood cell destruction attributable to the Mosaic or Hancock II valve. Hemolysis will be diagnosed by plasma free hemoglobin higher than the upper limit of the normal range (to be determined by the lab), or plasma free hemoglobin > 40mg/dl on 2 consecutive measurements within 24 hours.
 
However, if plasma free hemoglobin results are inconclusive or not available, serum lactate dehydrogenase, haptoglobin and reticulocyte count may be used together to diagnose hemolysis.
 
Severity of hemolysis is classified as clinically significant (requires intervention (i.e., long-term iron supplement, transfusion, or replacement of bioprosthesis)) or not clinically significant (does not require intervention)
 
Events which are excluded are those due to liver disease or systemic infection. If the event is secondary to endocarditis, hemorrhage, perivalvular leak, thromboembolism, thrombosis, it should be reported as such.

Hemorrhage (bleeding)	
Any episode of internal or external bleeding. These events are reported as major or minor as defined below:
 
Major: An episode of internal or external bleeding with more than or equal than 1 liter blood loss which causes death, hospitalization, or permanent injury (e.g., vision loss) or necessitates transfusion 3 or more units of blood, pericardiocentesis, or reoperation.
 
Minor: All other episodes of internal or external loss of blood after 24 hours from index procedure. Examples include nosebleeds that require nose packing as outpatient or ER visit, hematomas due to trauma or surgery that do not require transfusion, or minor ocular hemorrhage.
 
Excluded from this definition are bleeding events associated with major trauma or a major operation. Bleeding events occurring during the index procedure, including any bleeding within 24 hours of index procedure with less than 3 units' blood transfusion, or less than 1 liter blood loss are excluded.
 
Anticoagulant/antiplatelet-related hemorrhage
 
All major or minor hemorrhage events in subjects who are receiving anticoagulants and/or antiplatelet drugs

Term	Valve-Related Adverse Event Definition
Nonstructural dysfunction	
Abnormality resulting in stenosis or regurgitation of the heart valve substitute that is not intrinsic to the valve itself. The diagnosis should be confirmed by examination of the explanted or damaged valve.
 
Examples include:
 
 
• Entrapment by pannus (ingrowth of tissue into the heart valve substitute which may interfere with normal functioning) or suture
 
• Paravalvular leak (clinically or hemodynamically detectable defect between the heart valve substitute and the patient's annulus),
 
• Inappropriate sizing,
 
• Significant hemolytic anemia
 
 
This dysfunction is exclusive of valve thrombosis, systemic embolus, or infection diagnosed at re-operation, autopsy, or in vivo investigation.

Paravalvular leak	
Any evidence of leakage of blood around the prosthesis between the sewing ring and the native annulus. Paravalvular leaks will be graded for severity of the regurgitation using the ASE Aortic Valve Regurgitation scale (see Section 2.4) and will be classified as:
 
Minor leaks: does not require surgical or percutaneous intervention
 
Major leaks: requires surgical or percutaneous intervention
 
Clinically significant paravalvular leak (PVL that is moderate or greater in severity as assessed by the ASE Aortic Valve Regurgitation scale (see Section 2.4) and/or requires reintervention) as assessed by the site should be reported as an adverse event.
 
If the event is secondary due to endocarditis, it must be reported as such. Secondary events related to paravalvular leak (hemolysis, thromboembolism, or thrombosis) should be also be recorded as such.
 
For study progress reports and regulatory submission, all paravalvular leak regardless of severity will additionally be summarized as assessed by the Echocardiography Core Lab for each subject at each visit.

Structural Valve Deterioration viii	
Change to the function of a heart valve substitute resulting from an intrinsic abnormality that causes stenosis or regurgitation. The diagnosis should be confirmed by examination of the explanted or damaged valve.
 
It includes intrinsic changes such as wear, fatigue failure, stress fracture, calcification, leaflet tear, and stent creep.
 
 
• This definition excludes paravalvular leak infection or pannus overgrowth, or thrombosis of the heart valve substitute as determined by reoperation, autopsy, or in vivo investigation.
 

Term	Valve-Related Adverse Event Definition
Thromboembolism viii	
Clot or other particulate matter, not associated with infection, originating on or near the heart valve substitute and transported to another part of the body. Diagnosis may be indicated by:
 
 
• A new, permanent or transient, focal or global neurologic deficit (exclusive of hemorrhage)
 
• Any peripheral arterial embolus unless proved to have resulted from another cause (e.g., atrial myxoma);
 
• Acute myocardial infarction that occurs after operation in patients with known normal coronary arteries.
 
 
Events which are excluded are:
 
 
• Neurologic deficit resulting from hemorrhage
 
• Patients who do not awaken post-operatively or who awaken with a stroke or myocardial infarction are excluded.
 
• Any peripheral arterial emboli proven to have originated from another cause (e.g., atrial myxoma), pulmonary emboli, or events due to proven ischemic disease of the extremities.
 
• Acute myocardial infarction that occurs after operation in with known coronary artery disease.
 
 
If the event is secondary to hemorrhage, paravalvular leak or endocarditis, it should be reported as such. Secondary events related to thromboembolism should also be recorded as such.

Thromboembolism, cont.	
Neurologic events: viii
 
Any central, new neurological deficit, whether temporary or permanent, focal or global, that occurs after the patient emerges from anesthesia.
 
 
• Transient ischemic attack (TIA) is a fully reversible neurologic event that lasts less than or equal to 24 hours. If radiographic imaging demonstrates an acute central neurologic lesion (cerebral infarction with transient symptoms"), the event should be reported as a stroke. Multiple or repeated transient events occurring during a short period (a burst or cluster) should be reported as one event and documented as a cluster.
 
• Stroke (CVA) is a neurologic deficit lasting more than 24 hours, or lasting 24 hours or less with brain imaging study showing infarction.
 

	
Peripheral embolic events: ix
 
An operative, autopsy, or clinically documented embolus that produces symptoms from complete or partial obstruction of a peripheral (noncerebral) artery.
 
Acute myocardial infarction: ix
 
An area of coagulation necrosis resulting from impaired oxygenation of the myocardium.

Term	Valve-Related Adverse Event Definition
Valve Thrombosis	Blood clot not associated with infection, causing dysfunction of the heart valve substitute. Diagnosis may be proven by operation, autopsy, or clinical investigation (e.g., echocardiography, angiography, or MRI)

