**Table 7. Expected Occurrence of Valve Related Events per OPC**

Adverse Event	Bioprosthetic	
	Aortic	Mitral
Thromboembolism	1.5%	1.3%
Valve Thrombosis	0.04%	0.03%
Major Haemorrhage - Anticoagulant related	0.6%	0.7%
Major Paravalvular Leak	0.3%	0.2%

Endocarditis	0.5%	0.4%
--------------	------	------

There are no expected additional risks due to subject participation in the study. Preoperative evaluation and close postoperative monitoring will minimize foreseeable risk and discomfort. Interactions with concomitant therapy may exist. See the IFU for a list of contraindications.

The following measures will be implemented to minimize risks to study subjects:

- Investigators will have expertise in aortic and/or mitral heart valve replacement procedures.
- Investigative sites will have comprehensive cardiology and surgery programs.
- Investigators will be trained on the use of the Mosaic and Hancock II valves with PEEK material and accessories.
- Instructions for Use are provided with each Mosaic and Hancock II device to ensure consistent use of the device within pretested parameters.
- Subjects receiving the Mosaic or Hancock II valves with PEEK material will be rigorously followed over the course of the study by appropriately trained personnel. The protocol includes regular follow-up visits to assess device safety. These visits will enable detection of deterioration in Mosaic and Hancock II valves with PEEK material function should it occur, and allow appropriate intervention. The safety events will be closely reviewed by a panel of expert physicians (Clinical Events Committee).

Potential treatments for the foreseeable risks may include medication, surgery, medical monitoring or other applicable treatments, and will be provided at the discretion of the Investigator.

Any unanticipated or unforeseen complications will be reported by the PI (or authorized designee) to the Ethics Board and to Medtronic. Medtronic will in turn report any necessary findings to the appropriate regulatory agencies/bodies in each of the respective geographies.

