### 12.1.2. Evaluation and Documentation of Adverse Events and Device Deficiencies

Investigators are required to evaluate and document in the medical record all AEs and Device Deficiencies (per the definition in Table 8) observed in study subjects from the time they are enrolled until they are no longer participating in the trial. Regarding Adverse Event collection, the study is deviating from ISO 14155:2011 as in the scope of the study Investigators are required to report the following reportable Adverse Events to Medtronic: all Serious Adverse Events, all device and procedure related Adverse Events and all Device Deficiencies.

All reportable Adverse Events / Device Deficiencies that occur from subject enrollment through subject exit need to be reported to Medtronic via the appropriate eCRFs.

In addition, for all deaths and potential primary safety endpoint-related adverse events, sites should submit relevant, de-identified source documents to Medtronic for the Clinical Events Committee (CEC) members to use in their adjudication of the event. The CEC may request source documentation on additional events, at their discretion and according to the CEC Charter. Additional information regarding the CEC is detailed in Section 13.

The events listed in Table 9 are expected for patients undergoing cardiac surgery, and do not need to be reported as an AE, unless they occur outside of the stated timeframe, are otherwise considered to be an AE according to the treating Investigator, or are suspected or confirmed to be device-related.

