**Table 9. Non-Reportable Medical Occurrences Associated With Index Procedure**

Body category	Occurrence	Timeframe (hours) from the Index Procedure
Hematologic	Blood transfusion and anemia occurring during the index procedure within expected ranges (part of the regular hospital protocol)	0
Hematologic	Any bleeding during the index procedure	0
Hematologic	Any bleeding after index procedure with < 3 units blood transfusion, or < 1 liter blood loss	24
Cardiac	Short transient episode of arrhythmia (including ventricular fibrillation) during index procedure	0
Central nervous system	Confusion, anxiety and/or disorientation (other than TIA/stroke) starting within 48 hours with or without medical intervention	120 (5 days)
Central nervous system	Temporary change in mental status (other than TIA/stroke) not requiring additional medical interventions or new medical assessments (e.g. CT)	72
Central nervous system	Dizziness and/or lightheadedness with or without treatment	24
Central nervous system	Headache with or without treatment	72
Central nervous system	Sleep problems or insomnia with or without treatment	120 (5 days)
Respiratory/pulmonary	Mild dyspnea or cough with or without treatment	72
Respiratory	Oxygen supply after extubation / "forced breathing therapy"	48
Gastrointestinal	Diarrhea with or without treatment	48
Gastrointestinal	Obstipation / Constipation with or without treatment	72
Gastrointestinal	Anesthesia-related nausea and/or vomiting with or without treatment	24
Body Temperature	Low-grade fever (<101.3°F or <38.5°C) without confirmed infection	48
Body Temperature	Low body temperature	6
Pain	Pain (e.g. back, shoulder) related to laying on the procedure table with or without treatment	72
Pain	Incisional pain (pain at access site) with or without standard treatment and patient not returning to clinic to have additional treatment	No time limit
Pain	Pain in throat and/or trachea due to intubation	72
Skin and subcutaneous System	Mild to moderate bruising or ecchymosis	168 (7 days)
Respiratory	Atelectasis / Pleural Effusion not requiring punctuation	168 (7 days)

Body category	Occurrence	Timeframe (hours) from the Index Procedure
General	Edema resulting in weight increase up to 4 kg / 9lbs from baseline	168 (7 days)

For all reportable events, the general procedure for Investigator reporting any adverse event is as follows:

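### The 1-litre condition in the major-haemorrhage definition grades some fatal or disabling bleeds as minor, and the *or* in the 24-hour exemption drops early bleeds that reach one of its two limits

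*Protocol*

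**What the plan says.** Protocol Section 18.5.2.3 opens its definition of major haemorrhage with "An episode of internal or external bleeding with more than or equal than 1 liter blood loss which causes death, hospitalization, or permanent injury", gives vision loss as an example of permanent injury, and continues "or necessitates transfusion 3 or more units of blood, pericardiocentesis, or reoperation". Minor haemorrhage is the residual class: "All other episodes of internal or external loss of blood after 24 hours from index procedure".

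The same entry sets aside bleeding during the index procedure and then says that "any bleeding within 24 hours of index procedure with less than 3 units' blood transfusion, or less than 1 liter blood loss are excluded". Table 9 lists a matching non-reportable occurrence with a 24-hour timeframe: "Any bleeding after index procedure with < 3 units blood transfusion, or < 1 liter blood loss".

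Section 12.1.2 restores reporting of Table 9 items that fall outside the timeframe, "are otherwise considered to be an AE according to the treating Investigator, or are suspected or confirmed to be device-related". The same section requires investigators to report "all Serious Adverse Events, all device and procedure related Adverse Events and all Device Deficiencies".

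Table 7, in the risk section, gives an expected rate for "Major Haemorrhage - Anticoagulant related" of 0.6% in the aortic and 0.7% in the mitral position.

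**The concern.** Two pieces of logic look wrong.

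First, 1 litre of blood loss is written as a property of the episode, so it becomes a condition on the harm that follows. A bleed can kill or disable at far smaller volumes. The definition's own example, vision loss, sits poorly with a 1-litre minimum. Its examples of minor bleeding (minor ocular bleeding, haematomas not needing transfusion) suggest that the author meant worse bleeds of those kinds to be major.

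Second, an exemption meant for small early bleeds is met when either limit is missed. An early bleed stays in only if it reaches both 1 litre and 3 units.

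At stake is the safety description of the PEEK valves. Section 11.1 expects event rates similar to those of existing valves, and major anticoagulant-related haemorrhage is one of the five events in Table 7. Anticoagulant-related haemorrhage takes in both grades, so the grade alone decides whether such a bleed can be set against that Table 7 row. Section 13 leaves events other than deaths and potential primary endpoint events to the sponsor's safety staff, so for most non-fatal bleeds this text is the main control on grading.

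**Working it through.** The plan states no figure here to reproduce, so the check is of logic, followed by a calculation of scale.

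**Step 1: the grade after 24 hours.** Let L = loss of at least 1 litre; H = death, hospitalization or permanent injury; T = need for at least 3 units, pericardiocentesis or reoperation. The sentence can be read two ways:

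- Reading A (natural grammar; the litre governs both verbs): major = L and (H or T).
- Reading B (the litre governs only the harm limb): major = (L and H) or T.

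The last column makes the litre a separate criterion: major = L or H or T.

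| L | H | T | Reading A | Reading B | Litre separate |
|---|---|---|---|---|---|
| no | no | no | minor | minor | minor |
| no | yes | no | minor | minor | major |
| no | no | yes | minor | major | major |
| no | yes | yes | minor | major | major |
| yes | no | no | minor | minor | major |
| yes | yes | no | major | major | major |
| yes | no | yes | major | major | major |
| yes | yes | yes | major | major | major |

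The second row is minor on both readings. It is the fatal or disabling sub-litre bleed without treatment need. The third and fourth rows are minor only on Reading A.

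**Step 2: bleeds within 24 hours after the procedure.**

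| Loss | Units | Excluded with *or* | Excluded with *and* |
|---|---|---|---|
| 0.5 L | 1 | yes | yes |
| 0.9 L | 6 | yes | no |
| 2 L | 2 | yes | no |
| 1.5 L | 4 | no | no |

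Suppose the 2-litre, 2-unit bleed also needs reoperation. L and T are then both true, so it meets the major criteria on both readings, yet the exclusion removes it because fewer than 3 units were given.

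**Step 3: reporting.** The exceptions to Table 9 in Section 12.1.2 are timing, investigator judgement and device-relatedness. Seriousness is not among them. Table 8 makes an event serious if, among other things, it led to death, permanent impairment or prolonged hospitalization. An early bleed can therefore be exempt under Table 9 and reportable as an SAE under the same section, and no rule says which prevails.

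**Step 4: scale.** Section 11.1 describes the Table 7 rates as linearized; I read them as events per 100 patient-years (assumption). With 100 implanted subjects:

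- No attrition: 100 × 3 = 300 patient-years; 300 × 0.006 = 1.8 and 300 × 0.007 = 2.1 events.
- 10% lost per year (protocol synopsis), evenly within each year: 95.0 + 85.5 + 77.0 ≈ 257; 257 × 0.006 = 1.5 and 257 × 0.007 = 1.8.
- 20% lost in year 1 (the SAP's upper allowance), then 10% per year (assumption): 90.0 + 76.0 + 68.4 = 234.4; × 0.006 = 1.4 and × 0.007 = 1.6.

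One bleed moved from major to minor changes the observed rate by 1/300 = 0.33 to 1/234.4 = 0.43 per 100 patient-years, against reference rates of 0.6 to 0.7. This shows how much one event weighs. It does not estimate how many would be misgraded.

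**The case against.** The strongest reply has four parts.

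1. A reader might infer that the litre governs every criterion. The text does not settle this. On Reading B, the transfusion, pericardiocentesis and reoperation limb stands on its own. That is fair, but the second row of the first table is misgraded either way.

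2. A reader might infer that fatal or serious bleeds go unreported. The documents do not support that. All SAEs are reportable, investigator judgement or suspected device-relatedness restores Table 9 items, and Section 13 makes review of all deaths the minimum task of the Clinical Events Committee. For serious early bleeds the defect is a conflict between rules. The clear loss is a non-serious early bleed that misses one limit.

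3. The *or* exemption is the exact complement of at least 1 litre and at least 3 units, and Table 9 matches the definition, so a joint threshold may be deliberate. On Reading A this explains why 0.9 litre with 6 units is left out. It does not explain the 2-litre, 2-unit bleed needing reoperation, which meets the major criteria on both readings.

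4. No planned analysis uses the grade. The historical controls in protocol Section 14.2.3 cover only valve-related death, reoperation and explant, the SAP contains no haemorrhage analysis, and Table 7 sits in the risk section. This stands, and it limits the consequence.

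**Conclusion.** The definition should be corrected. On any reading it grades as minor a fatal or permanently disabling bleed under 1 litre after 24 hours that needs no major treatment. The 24-hour exemption removes early bleeds that reach one of its own limits.

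The consequence is bounded. The primary endpoint is untouched, because valve-related mortality in Section 18.5.2.2 names death from a bleeding event with no volume limit. What may suffer is the reported count of major bleeds, any informal comparison with Table 7, and consistency between sites in reporting early bleeds.

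It is tempting to conclude that the PEEK valves will look safer than the reference. The documents support only that they may: they do not give the haemorrhage definition behind the Table 7 rates, and no formal comparison is planned. Nor do they say what share of serious bleeds involves less than 1 litre, so the bias cannot be sized. The expected count of about 1.4 to 2.1 rests on reading Table 7 as rates per 100 patient-years, on 100 implanted subjects, and on the attrition assumptions shown.

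**What to change.** Make three changes in one edit:

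1. In Section 18.5.2.3, list loss of 1 litre or more as one of several alternative criteria for major haemorrhage, so that it no longer conditions death, hospitalization, permanent injury or the treatment-need limb.
2. In the 24-hour exclusion and in Table 9, exempt a bleed only when it is below both limits and meets no other major criterion.
3. In Section 12.1.2, state that Table 9 does not override SAE reporting.

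The changes depend on each other. If only *or* became *and*, an early bleed of 0.9 litre with 6 units would, on Reading A, be neither major, minor nor excluded. An early bleed of 0.5 litre with 2 units needing pericardiocentesis would still be excluded. With all three changes, every early post-procedure bleed covered by the definition is either exempt or major, and every later one is major or minor.

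The cost is definition wording and matching eCRF help text, a few more early bleeds to report, and a slightly higher major-bleed count. Part of that increase comes from bleeds of 1 litre or more with no other criterion, which are not major on either reading today.
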